Additional funding has allowed for the expansion of recruitment size; the current goal is to recruit 160 treatment group subjects and 160 control group subjects. Treatment and control group subjects will both be given an incentive of \$50.00 in cash for their participation in the survey, and control group subjects will also be given a gift basket filled with approximately \$75.00-\$100 worth of developmentally-appropriate gifts for their impending child (items are purchased from Amazon, and prices vary depending on when items are purchased). Approximately, four business days after the in-home visit, Columbia staff will let control group participants know that they were not selected for the Room to Grow Program; subjects in the treatment group will receive follow-up from Room to Grow. Experienced interviewers will conduct the interviews in either English or Spanish. Subjects will be enrolled in the "Columbia Moms and Babies Study" and follow-up permission and information will be collected during the baseline visit (i.e., subjects will be asked for best modes of future contact and have the opportunity to provide friends' and family members' contacts, email addresses, etc.). Additionally, to inform understanding of program operations and potential outcomes, 9 RtG program graduates will be invited to participate in Focus Groups; 20 RCT participants will be randomly selected and invited to participate in qualitative interviews; the three clinicians at Room to Grow will be invited to participate in qualitative interviews. An in-person visit will be completed with enrolled subjects that have completed the 42M phone survey, once the subject's focal child is at least 3 ½ years old. At the end of the 42M survey, study participants are informed of an opportunity to participate in the in-person visit conducted by the Columbia study team at the School of Social Work. We will also offer study participants the option to have the in-person visit take place in their home. New York City residents will be eligible for the visit. We will also have a handful of subjects who no longer live in NYC during the in-person visit phone contact. If any one of these subjects are living outside of NYC & are within reasonable traveling distance to/from Columbia University's School of Social Work or Nash Building, they too will be eligible for the visit.

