Additional funding has allowed for the expansion of recruitment size; we have recruited and enrolled 160 treatment group subjects and 160 control group subjects. Treatment and control group subjects will both be given an incentive of \$50.00 in cash for their participation in the 45 minute survey, and control group subjects will also be given a gift tote filled with approximately \$75.00-\$100 worth of developmentally-appropriate gifts for their impending child (this being the only difference between the treatment and control group consent forms attached to the protocol – the different versions of the consent forms only differ in their description of the compensation offered). Study participants who are selected in the RtG lottery will receive a follow-up call from RtG informing them of their selection, and Columbia staff will call the participants who do not receive a place in the lottery and invite them to remain part of the study approximately four business days after completing the baseline survey.

Experienced interviewers will conduct the interviews in either English or Spanish. Subjects will be enrolled in the “Columbia Mothers and Babies Study” and follow-up permission and information will be collected at that point (i.e., subjects will be asked for best modes of future contact and have the opportunity to provide friends’ and family members’ contacts, email addresses, etc.). Approximately 4 months after the completed baseline interview, subject will be mailed a jotter and a letter with Columbia’s contact information so that participants can reach out with updated contact information. Approximately 9-10 months after the baby is born, participants who agreed will be followed up with on the phone and will be asked to participate in a 40 minute survey with a \$35 incentive. Due to the transient nature of this study sample, we anticipate that it will be more difficult to reach some subjects than others. For subjects that do not refuse, but who have not completed the follow-up survey after 10 attempts, we will be offer an additional \$15 incentive, bringing the total compensation to \$50.

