Subjects enrolled in the study who consented to future follow-up will again be contacted when their babies are 25 months and invited participate in a 45 minute phone survey with a \$40 incentive. In line with procedures from the 10 month follow-up, subjects that do not refuse, but who have not completed the follow-up survey after 10 attempts, will be offered an additional \$15 incentive, bringing the total compensation to \$55.

\*Added 12/2/2020\*

Subjects enrolled in the study who consented to future follow-up at 25M, will again be contacted when their babies are 42 months old. They will be invited to participate in a 55-minute phone survey with a \$40 incentive. In line with procedures from the 10-month follow-up and 25 month follow-up, subjects that do not refuse, but who have not completed the follow-up survey after 10 attempts, will be offered an additional \$15 incentive, bringing the total phone survey compensation to \$55 for these subjects.

Due to the transient nature of this population, we anticipate that a small percentage of subjects will no longer be living with their babies at the 9-10 month or 25-month follow-up. We will make an effort to keep these subjects in the study, as they offer valuable insight into a subset of the population. Subjects will be invited to participate using the same protocol, and the same approved 10M or 25M survey. All subjects will be asked if they are living with their babies. If a subject indicates that they are not living with their baby, the survey version they are administered will omit sections pertaining to child and family routines. Subjects will still be surveyed on sections pertaining to maternal health, hardship and employment. Subjects will still receive full compensation for their participation.

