#### CONSENT BOOKLET FOR LINKAGE TO ADMINISTRATIVE DATA:

The consent booklet (located on pages 4-7) outlines the types of administrative data (NYC Department of Education AND Administration for Children's Services (ACS)/ Child Protective Services (CPS)/ Statewide Central Register of Child Abuse and Maltreatment (SCR) records we hope to link to the survey and in-person visit assessment data. Staff will, either before or after the assessments, review the consent booklet with the parent, and will ask him/her to read over the booklet and decide whether or not to consent for linkage to each type of data.

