#### 25 Month Follow-Up Recruitment Strategy

Using the subject's projected due date, Columbia staff will initiate phone contact with subjects who agreed to be contacted for follow-up approximately one week before their baby is 25 months old. Columbia interviewers will use the most up to date contact information available (from the 10 month follow-up and baseline interview). At this point in the study, all enrolled mothers will be 18 years of age or older, thus only adult recruitment and consent procedures will be used by experienced interviewers.

Interviewers will call and remind subjects of the purpose of the study, describe what the follow-up entails and invite them to participate using the attached 25M phone pitch. The subject can agree to participate at the time of the call or can schedule the survey at a later time. A subject is free to refuse participation in the follow-up. If the subject agrees, a consent script will be read verbatim and verbal informed consent will be obtained at the start of the survey (see attached 25M Phone Consent).

Once we make contact with the subject on the phone we will use previously approved protocols to pitch, schedule and complete the 25 month survey with the subject's consent. These same procedures will be used to pitch, schedule and complete the 42 month survey with the subject's consent.

For subjects who indicate they are no longer living with their child, and voluntarily provided contact information for the new primary caregiver of the child, interviewers will call and explain to the primary caregiver the purpose of the study and invite them to participate using the 25M PCG phone pitch. If the PCG agrees to participate, a consent script (see attached PCG Phone Consent) will be read verbatim and verbal informed consent will be obtained at the start of the survey.

\*Added 4/14/2021\*

For subjects who indicate they are no longer living with their child and voluntarily provided contact information for the primary caregiver of the child or if the study team already has contact information for the primary caregiver, interviewers will call and explain to the primary caregiver the purpose of the study and invite them to participate using the 42M PCG phone pitch. If the PCG agrees to participate, a consent script will be read verbatim and verbal informed consent will be obtained at the start of the survey.

IN-PERSON VISIT:

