**Describe how participants' consent will be obtained and whether an information sheet will be used:**

During the scheduling call, subjects are informed of the voluntary nature of the study and are invited to set up a time to meet for the baseline survey; at the time of the meeting formal written consent will be obtained before proceeding with the baseline survey or any further study participation.

During recruitment for the 10 month follow-up, 25 month follow-up, & 42 month follow-up, subjects who agreed to follow-up at baseline will be called and invited to participate in the follow-up phone survey. Because the survey will be conducted over the phone, interviewers will read an informed consent script and obtain verbal consent from the subject before proceeding with the survey. Subjects will be informed of their right to refuse participation and the right to skip any question. All materials will be translated to Spanish and interviewers who are fluent in Spanish will obtain consent and conduct interviews with Spanish-speaking subjects.

Subjects will be invited to participate in an in-person visit once their child is at least 3 1/2 years old and once they have completed their 42 month follow-up survey. They may refuse to participate in the visit. Written consent for participation in the in-person visit activities with the child (EF-Touch, ROWPVT-4, and the 3 Bag Task) and parent will be obtained at the meeting, which will take place at Columbia University. A separate informed consent script will read to the subject for the in-person follow-up survey. The lead staff member will obtain verbal consent from the subject before proceeding with the survey. Subjects will be informed of their right to refuse participation and the right to skip any question. All materials will be translated to Spanish and interviewers who are fluent in Spanish will obtain consent and conduct interviews with Spanish-speaking subjects. We will obtain written/documented consent if a study participant completes a paper version of our in-person survey and mails it back.

---

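### The protocol gives conflicting rules for who is called at 42 months; under the stricter one, a missed or refused 25-month wave also costs the child assessments and record linkage

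*Combined protocol and SAP*

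**What the plan says.** Section 2 reports enrolment as complete: "we have recruited and enrolled 160 treatment group subjects and 160 control group subjects".

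**25 months.** The rule is "Subjects enrolled in the study who consented to future follow-up will again be contacted when their babies are 25 months". The 25 Month Follow-Up Recruitment Strategy draws contact details from both baseline and the 10-month wave. Nothing makes the 25-month call depend on a completed 10-month survey.

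**42 months.** Four places bear on who is called:

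- Section 2, paragraph added 12/2/2020: "Subjects enrolled in the study who consented to future follow-up at 25M, will again be contacted when their babies are 42 months old".
- The description of how consent will be obtained: "During recruitment for the 10 month follow-up, 25 month follow-up, & 42 month follow-up, subjects who agreed to follow-up at baseline will be called".
- Informed Consent Process: the 42-month procedures follow those of the earlier waves and cover mothers who agreed to be contacted. It does not say at which wave they agreed.
- 25 Month Follow-Up Recruitment Strategy: its procedures are carried over to 42 months, with no added condition about consent at 25 months.

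**Visit.** Study Design states: "An in-person visit will be completed with enrolled subjects that have completed the 42M phone survey". The consent description repeats this condition, and the recruitment text places the invitation at the end of the 42-month survey.

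**Linkage.** The linkage booklet section says: "Staff will, either before or after the assessments, review the consent booklet with the parent". The Data paragraph of Study Design also mentions linkage consent together with the visit. No other route is described.

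**The concern.** The two explicit 42-month rules define different samples. Under the section 2 rule, a mother who was unreachable or declined at 25 months is not approached at 42 months, even if she gave permission at baseline and could be found again. The loss then carries forward: without a 42-month survey there is no visit, and without a visit no described occasion to consent to linkage. The receptive vocabulary, executive function and three-bag outcomes, and the education and child-welfare records, would come from a subset defined by response after randomisation.

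The protocol itself expects some of these mothers to be hard to reach. Its Statistical Procedures section concedes limited power and gives neither a retention assumption nor a method for missing data. Avoidable loss therefore falls on a trial with little margin, and nothing in the analysis plan addresses it.

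**Working it through.** **Step 1. Compare the rules.** The 25-month rule in section 2 asks only for consent to future follow-up. The 42-month rule in the same section adds a reference to 25 months. The natural reading is that the addition sets a new condition: consent given at the 25-month wave. The consent description puts 10, 25 and 42 months on one footing, agreement at baseline. A mother who agreed at baseline but was missed at 25 months is called under one rule and not under the other.

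**Step 2. Trace the consequence under the section 2 rule.** 25 months missed or refused → not called at 42 months → no 42-month survey → not eligible for the visit → no child assessments and no described request for linkage consent. Under the baseline rule the chain breaks at its first link.

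**Step 3. Illustrate the size.** The plan has no figure to reproduce: it states no retention rate, effect size, SD or power. The documents supply 160 per arm, so 320 in total. Everything else is assumed:

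- all 320 gave baseline permission;
- 75–85% respond at 25 months, and all of those consent to further contact;
- 80–90% of those called under the strict rule complete 42 months;
- 30–50% of 25-month non-responders could be reached at 42 months;
- response is equal in the two arms.

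The minimum detectable difference in SD units is (1.960 + 0.842) × √(2/n per arm), for two-sided 5% and 80% power. With no loss, n = 160 gives 0.313.

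| | 75% at 25 months, then 80% | 85% at 25 months, then 90% |
|---|---|---|
| Respond at 25 months | 320 × 0.75 = 240 | 320 × 0.85 = 272 |
| Not called at 42 months, strict rule | 320 − 240 = 80 | 320 − 272 = 48 |
| Complete 42 months, strict rule | 240 × 0.80 = 192 | 272 × 0.90 = 244.8 |
| Regained, 30% reachable | 80 × 0.3 = 24 | 48 × 0.3 = 14.4 |
| Regained, 50% reachable | 80 × 0.5 = 40 | 48 × 0.5 = 24 |
| Complete 42 months, baseline rule | 216–232 | 259.2–268.8 |
| Per arm, strict → baseline | 96 → 108–116 | 122.4 → 129.6–134.4 |
| Detectable difference, SD | 0.404 → 0.381–0.368 | 0.358 → 0.348–0.342 |

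The regained mothers are 14.4/320 = 4.5% to 40/320 = 12.5% of those randomised.

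**Step 4. Carry this to the visit.** If regained mothers attended at an assumed 60–80%, the visit would gain 14.4 × 0.6 ≈ 9 to 40 × 0.8 = 32 families. This is probably generous, because mothers already missed once may attend less often.

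**The case against.** The strongest reply is that the exclusion rests on one phrase. That phrase can also be read as consent to the follow-up held at 25 months, and none of the other three places repeats a 25-month condition. On that view there is a drafting slip and no demonstrated loss of families. This stands in part: the documents do not show which rule was used. It does not remove the need to reconcile them, because the natural reading of section 2 excludes mothers whom the consent description includes.

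Some stronger readings are tempting but not supported:

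- *One missed call removes a family.* It does not. In each phone wave, mothers who have not refused and have not completed after 10 attempts are offered a further $15. Only a missed or refused wave matters.
- *Every wave depends on the one before.* It does not. Missing 10 months alone removes nobody.
- *Linkage formally requires a completed 42-month survey.* No sentence says so. The dependence is inferred from where the consent is described.
- *Attrition will differ by arm.* The program meets treatment families every three months for three years, a period that covers the 25-month wave, so this is plausible. But Columbia staff make the follow-up calls from details given to Columbia, no text says the program supplies contact details, and its services end before 42 months.

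It is also fair to say that most non-response at 42 months and non-attendance at the visit would occur under either rule. Linkage needs parental consent, so a family that cannot be reached cannot be linked.

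**Conclusion.** The conflict is real and should be resolved. If section 2 is followed on its natural reading, mothers who missed or refused 25 months are excluded from 42 months and, through the later conditions, from the visit and the linkage request. The late comparisons then rest on a response-selected subset.

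On the assumed rates, 48–80 of 320 mothers would not be called and about 14–40 could be regained at 42 months. The gain in precision is modest, roughly 0.01–0.04 SD in the detectable difference. The larger reason to act is to keep the late samples as close as possible to the randomised groups. A reader might infer a known bias in the late outcomes. The documents do not support that, because its direction and size depend on response by arm, for which they give no data.

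**What to change.** Amend the 12/2/2020 paragraph of section 2 to match the consent description: at 42 months, contact every randomised mother who gave baseline permission and has not withdrawn, whether or not she completed 25 months. Use the same wording in Informed Consent Process and in the recruitment section. Check it against the scope of the permission in the baseline consent form, which is not among the pages available here. Report, by arm and wave, the numbers eligible, contacted, refusing and completing. If 42-month calls have already been made, state which rule was applied and how many mothers in each arm were not approached because of it.

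The cost is a protocol modification, extra calls by the existing survey team and some incentive payments.

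Optionally, offer the visit and the linkage booklet to reachable mothers who did not complete the 42-month survey. This needs IRB and agency acceptance, which cannot be judged from the documents: the booklet covers child-protection records and is now reviewed with staff, so a mailed or electronic route would change that consent process.

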#### Qualitative Data Gathering

The study will also include a qualitative component including focus groups with up to 9 RtG graduates and qualitative interviews with 20 randomly selected RCT participants (10 control and 10 treatment), and the three RTG clinicians.

We will conduct qualitative interviews with randomly selected study participants after they have completed the 10 month follow-up survey. Columbia research staff will randomly select 10 control group and 10 treatment group participants and invite the subjects to participate in a qualitative sub-study. A qualitative interview guide and revised consent form are attached in the documents section. The qualitative sub-study is intended to provide richer and more nuanced information about the circumstances of mothers and babies living in New York City and the impact that the Room to Grow has on enrolled families. The qualitative interviews will be 45-60 minutes in duration and \$40 in cash will be provided to the subjects as compensation. Subjects will be informed that participation in the sub-study is voluntary, and if they are in the treatment group, refusal will not

impact their Room to Grow services. Qualitative interviews will be conducted in the subject's home or an agreed upon location with trained Columbia staff.

We will recruit a maximum of 9 new participants that already graduated from Room to Grow (finalized the three-year program) to gather qualitative information about the impact that RtG had on their children and themselves and how the program could be improved. Because these participants have graduated from RtG it is important to capture their perspective. Graduated participants will be interviewed in focus groups of 4-5 participants. Finally, we will also interview the three clinicians serving families at RtG with the same purpose. All participants will be informed of their rights, including their ability to withdraw at any time and skip any question. Furthermore, current participants and clinicians will be reminded that their answers and participation status will have no bearing on their current Room to Grow services or employment.

#### IN-PERSON VISIT:

The in-person/home visit will take place either at the study participant's home or on campus. Using the Scheduling Script, staff will either call or email the parent & discuss the in-person visit activities. Staff will encourage or request that the visit be conducted on Columbia campus if the study participant's home (space) is too small or lacks privacy (e.g. the study participant rents a room in someone else's apartment) or if there has been a bedbug infestation within the last 60 days.

#### IN-PERSON VISIT CONSENT FORM:

The consent form (located on pages 1-3) explains & breaks down the visit into 2 parts:

Part 1: Purpose, procedures, compensation, risks & benefits of the study. The form also explains the ROWPVT-4 and executive function activities for the child, as well as the follow-up survey with the parent.

Part 2 : Explains the videotaping component for the parent & child during the "3-bag" activity. Staff will read this form thoroughly, answer any questions & address any concerns the subject may have.

Note, a separate consent form will be read to the parent before starting the follow-up survey.

#### CONSENT BOOKLET FOR LINKAGE TO ADMINISTRATIVE DATA:

The consent booklet (located on pages 4-7) outlines the types of administrative data (NYC Department of Education AND Administration for Children's Services (ACS)/ Child Protective Services (CPS)/ Statewide Central Register of Child Abuse and Maltreatment (SCR) records we hope to link to the survey and in-person visit assessment data. Staff will, either before or after the assessments, review the consent booklet with the parent, and will ask him/her to read over the booklet and decide whether or not to consent for linkage to each type of data.

